Primary Aim 1: To test whether CPT is more effective than IDC in treating symptoms of PTSD among Veterans and civilians with OUD maintained on buprenorphine. PTSD symptoms will be measured using the PTSD Checklist – Military version (PCL-5), and confirmed by the Clinician Administered PTSD Scale using the DSM-5 criteria (CAPS-5).

Secondary Aim 1: To test whether CPT- is more effective than IDC in reducing opioid use among Veterans and civilians with PTSD and comorbid OUD maintained on buprenorphine. Opioid use will be measured using the Timeline Follow-back (TLFB) and confirmed by urine toxicology results.

Exploratory Aims: To examine if treatment groups differ in 1) *retention*, measured by days in treatment, 2) *psychosocial functioning*, measured by the *participants RAND 12-Item Short Form Health Survey (VR-12)*, 3) *sleep* as measured by the *Insomnia Severity Index (ISI)*, since sleep disturbance is a hallmark of PTSD and during early abstinence from opioids, and 4) Because of the high comorbidity between PTSD and chronic pain we will explore this relationship and will measure *pain intensity* (measured by the Numeric Rating Scale (NRS), and *functional impairment* using the PROMIS-29 (Patient-Reported Outcomes Measurement Information System) longitudinally over the course of treatment. Follow up will be conducted 1 and 3 months after completion of the study to evaluate *durability of effect on PTSD symptoms (measured as changes in PTSD symptoms), opioid use and treatment utilization*.

4-5. BACKGROUND AND SIGNIFICANCE:

This proposal was originally developed in collaboration with the Consortium to Alleviate PTSD (CAP) ([name] Director and [name] co-Director), underwent scientific review and was proposed for funding. However, CAP was unable to fund it as buprenorphine treatment is of limited importance for active-duty personnel. The CAP leadership group encouraged our group to send this application to the VA as it has great clinical relevance for the VA and for Veterans, *although CAP is no longer involved in this proposal*. Please see the attached letter of support.

A. Posttraumatic stress disorder (PTSD)

i) PTSD is a serious psychiatric disorder that can occur after the experience of a traumatic event.

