The abuse of prescription opioids, including oxycodone, hydrocodone, hydromorphone, morphine, codeine, propoxyphene, and methadone, has emerged as a major public health problem particularly in the United States (US), which represents about 5% of the world's population but consumes 80% of the global opioid supply.[40] Prescriptions for opioid medications have increased dramatically over a 10 year period with

174 million prescriptions dispensed from retail pharmacies nationally in 2000, increasing to 257 million prescriptions by 2009. [41] Abuse or non-medical use of prescription opioids is defined as use without a prescription and/or in a manner other than intended or prescribed, and more than 12 million people reported using prescription opioids non-medically in 2010.[42] Unlike other drugs of abuse, prescription opioid medications are primarily obtained from physicians, friends or family members and/or the Internet, rather than through drug dealers.

Use of prescription opioids is associated with significant morbidity and mortality.[43] Deaths from prescription opioids have dramatically increased over the past 10 years and are now the second leading cause of accidental death in the US[44]. According to data from the Centers for Disease Control and Prevention (CDC), deaths due to prescription opioids went from 1.3 per 100,000 in 1999 to 5.0 per 100,000 in 2008, resulting in 14,800 prescription painkiller deaths in 2008.[6] As expected, exposure to opioids, including days of supply and higher doses of opioids, has been found to increase the risk of abuse and dependence.[45] A task force on prescription opioid non-medical use and abuse was convened by the College for Problems of Drug Dependence (2003). Their report confirms an increase in the incidence of prescription OUD, including survey data and from data collected regarding treatment admissions for drug abuse, based on the Treatment Episode Data Set (TEDS).[46] Many states showed an increase in incidence of 20% or more[46] over a 10 year period.

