Opioid prescription drug use has been shown to be a “gateway” to use of other drugs of abuse such as heroin.[47] As awareness of the prescription opioid epidemic increased, availability of prescription opioid medications has decreased and in its wake there has been an alarming increase in heroin use, with devastating morbidity and mortality. The rate of reported heroin use has doubled between 2006-2012[11] and there is a fourfold increase in heroin overdose deaths between 2000 and 2014.[12] [Further, the spike in overdose deaths is also due to a proliferation of other deadly drugs such as fentanyl.[48] This has led to a national crisis and as reported in the media, (e.g. The New York Times) and the **current administration recently declared the opioid epidemic an National Emergency.]**

The recent opioid epidemic has had a significant effect on Veterans mirroring the national trends [49] This may be in part due to iatrogenic factors. For example, pain conditions, are common among young Veterans, with report of almost 50% of patients in outpatient VA settings reporting pain primarily due to musculoskeletal injuries.[50] The prevalence of these injuries may be in part due to medical advances, since more military personnel are surviving war related complex injuries, including blast injuries and this results in an increase in the number of Veterans suffering from chronic pain. Treating chronic pain is challenging, as highly addictive prescription opioids have been the mainstay of treatment.[10] The rates of prescribed opioids increased dramatically over a 10-year period (2001-2009) among military personnel, a factor which was found to undermine military readiness.[8] This issue is particularly challenging in Veterans with trauma[51] and those diagnosed with PTSD, as they are more susceptible to developing substance use disorders.[8] Veterans with mental health disorders, notably PTSD, are more likely to be prescribed opioids, more likely to participate in high risk behaviors and more likely to have adverse outcomes.[9]

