6. RESEARCH PLAN

Research design and methods

Overview: We propose to conduct a randomized, controlled trial with 160 (assuming a 30% drop out rate, for 120 participants) Veterans and civilians diagnosed with PTSD and comorbid OUD. This study will use *open*

randomization to 2 groups: (a) buprenorphine + CPT vs. (b) *buprenorphine + IDC*. All subjects will be maintained on buprenorphine and the standard clinical treatment. Participants will be recruited primarily through the clinical facilities at the VA and from other collaborators.

The Bedford VAMC has been added as an additional enrollment site for this study. The principal investigator for the Bedford site is [name] and the study will be overseen by the Bedford VA IRB has gained local IRB approval.

Experimental subjects: Veterans and civilians (n=160) aged 18- 65 years old, with a current diagnosis of PTSD and opioid use disorder (OUD) will be enrolled at 2 sites (VA Connecticut Healthcare System, Bedford VAMC) for a study with 12-weeks of active treatment. Participants will be recruited from four main sources: 1) from the PTSD clinic patients at the local VAs , 2) from the group of Veterans entering treatment for opioid use disorders at the local VA Substance Abuse Treatment Programs and 3) advertisement (flyers, posters, Craigslist) 4. Community clinics. Under a HIPAA waiver, IRB-approved letters of invitation can be mailed to prospective participants with a past diagnosis of OUD or PTSD who otherwise might meet eligibility criteria. Outreach will also be conducted at local Veteran Centers, where staff from both VAs consult. The PTSD staff has also been involved in outreach to the community for returning OIF/OEF Veterans. Each participant will be carefully screened and assessed using the following inclusion and exclusion criteria:

Inclusion Criteria:

- 1) Male and female Veterans and civilians between the ages of 18-70 years old.
- 2) Current diagnosis of PTSD as determined by an independent evaluator assessment using CAPS-5.
- 3) Opioid Use Disorder diagnosed by Mini International Neuropsychiatric Interview for DSM-5 (MINI). To meet entry criteria for buprenorphine treatment, will also have documented prior treatment for opioid use disorder, history of opioid withdrawal or signs of opiate withdrawal as evidenced by a Clinical Opiate Withdrawal Scale (COWS) score of 7 or greater, and a positive urine toxicology for opioids.

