(k) Adverse Events (AE) will be assessed by the RN at each weekly assessment using Food and Drug Administration (FDA) standards for AE reporting. Serious Adverse Events (SAE) and Unanticipated Problems Involving Risk to Subjects or Others (UPIRSO) will be reported to the local IRB as well as to the DSMB and other authorities according to their standard reporting requirements.

(l) Pain will be measured during the clinical trial using recommendations from the consensus group that has published a large number of papers with recommendations for pain clinical trials called the Initiative of Methods, Measurement and Pain Assessment in Clinical Trials (IMMPACT)[92]. IMMPACT recommends an assessment of several key domains including pain intensity and functional interference. For pain intensity, a simple 11-point **Numeric Rating Scale (NRS)** has been recommended by IMMPACT and remains the gold standard in clinical trials. It is the VA's "5th vital sign" so participants will be familiar with it. Functional impairment due to pain will be measured using the **PROMIS-29 scale**.[93]

(m) Additional baseline characteristics will be assessed using the Life Events Checklist for DSM-5 (LEC-5), Child Trauma Questionnaire (CTQ), Cannabis Use History Questionnaire, and the Synthetic Cannabinoids Use History Questionnaire.

Confirmation of self-reported drug use: Urine toxicology screening will be done at every in-person MM visit and urine will be tested using Abbott Diagnostics CI8200 screen done at the VA Facility. The standard urine toxicology includes testing for amphetamines, barbiturates, benzodiazepines, cannabinoids, cocaine and oxycodone. Methadone and buprenorphine are ordered separately, but all will be included in the weekly

screening. Fentanyl is a separate test and will be ordered if a participant has a history of use/abuse. Testing for each of these substances uses immunoassays; if there is a question about accuracy, testing is confirmed using gas chromatography/mass spectroscopy. Urine drug testing is a routine part of buprenorphine maintenance treatment.

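### The protocol names no opiate-class urine assay, so, run as listed, the panel would leave heroin, morphine and codeine use unconfirmed

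*Combined protocol and SAP*

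**What the plan says.** The panel is set out only in section 6, Study Assessments, in the paragraph on confirming self-reported drug use:

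- Standard panel: "The standard urine toxicology includes testing for amphetamines, barbiturates, benzodiazepines, cannabinoids, cocaine and oxycodone".
- Routine additions: "Methadone and buprenorphine are ordered separately, but all will be included in the weekly" screening.
- Conditional addition: "Fentanyl is a separate test and will be ordered if a participant has a history of use/abuse".
- Method: "Testing for each of these substances uses immunoassays; if there is a question about accuracy, testing is confirmed using gas chromatography/mass spectroscopy".

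Other parts of the plan depend on this panel:

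- Secondary Aim 1 (Specific Aims): "Opioid use will be measured using the Timeline Follow-back (TLFB) and confirmed by urine toxicology results". The Primary and Secondary Hypotheses section repeats this for each medication visit and follow-up.
- Data Analysis treats the Timeline Follow-back (TLFB) and urine toxicology as the two measures in the opiate-use domain and sets the significance level there at 0.025.
- Inclusion criterion 3 includes "a positive urine toxicology for opioids" among its entry conditions.

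On the drugs of interest, both the Purpose section and Background part B say that as prescription opioids became scarcer, "in its wake there has been an alarming increase in heroin use". Background part B lists the prescription opioids of abuse, "including oxycodone, hydrocodone, hydromorphone, morphine, codeine, propoxyphene, and methadone", and adds fentanyl as a cause of overdose deaths.

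**The concern.** The plan uses urine toxicology as a measure of opioid use, but the only opioid in the listed standard panel is oxycodone. Of the assays ordered separately, buprenorphine is the treatment given to every participant, so a positive result on it does not show illicit use. That leaves oxycodone and methadone at every tested visit, and fentanyl for some participants.

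Allocation is open, and the TLFB is self-report by participants who know their arm. Urine is the only objective check on opioid use in the plan. If it does not look for heroin, under-reported heroin use has nothing to contradict it, and a difference between CPT and IDC in heroin use would not appear in the urine measure. An assay that was never run may not be recoverable at analysis.

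**Working it through.** There is no plan figure to reproduce. The check sets the named opioids against the named assays.

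| Opioid named in the background | Named urine assay |
|---|---|
| Oxycodone | Yes, standard panel |
| Methadone | Yes, ordered separately, routine |
| Fentanyl | Only with a history of use |
| Heroin | None |
| Morphine | None |
| Codeine | None |
| Hydrocodone | None |
| Hydromorphone | None |
| Propoxyphene | None |

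The count is 7 prescription opioids + heroin + fentanyl = 9 names: 2 tested routinely, 1 conditionally, and 9 − 2 − 1 = 6 with no named assay. This counts names in an epidemiology section. It is not a share of use in the trial sample.

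**Effect on the urine measure.** Let p be the true proportion of participants using a non-prescribed opioid at a visit, and s the share of those who use only opioids that no assay run on them detects. Someone who uses heroin and oxycodone is still detectable and does not count towards s. Taking the assays as otherwise accurate:

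- observed proportion positive = p × (1 − s)
- observed arm difference = p_IDC × (1 − s_IDC) − p_CPT × (1 − s_CPT)
- if s is the same in both arms, this is (1 − s) × (p_IDC − p_CPT), which is closer to zero than the true difference whenever s > 0 and the arms truly differ.

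With s = 0 nothing is lost; with s = 1 the whole difference is lost. If s differs between arms, the direction of the error is not fixed. The documents give neither the drug mix nor cross-reactivity data, so s cannot be narrowed from them.

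**Effect at entry.** Criterion 3 lists documented prior treatment, a history of withdrawal, or current withdrawal on the COWS, and then the positive urine. It can be read in two ways:

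1. (prior treatment or withdrawal history or COWS) and positive urine. A heroin-only entrant who is not on buprenorphine and has no fentanyl exposure then has no listed assay to be positive on.
2. prior treatment, or withdrawal history, or (COWS and positive urine). Such a person can then enter without the urine result.

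The Buprenorphine part of Standard Treatment also admits people already taking buprenorphine, who skip induction. Criterion 3 does not say whether a buprenorphine positive meets its urine condition. These passages need to be reconciled.

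**The case against.** A reader might infer that heroin use cannot be confirmed in this trial and that heroin-only users cannot be enrolled. The documents do not support that, for these reasons:

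- The panel sentence says the screen includes the named tests, which need not be exhaustive. An opiate assay may be run and simply not listed. This stands as a caveat, although the paragraph takes care to spell out even the separately ordered tests.
- No assay-performance data are given. That the oxycodone and methadone assays miss heroin is an assumption. The plan's separate naming of opioid tests makes it reasonable but does not prove it.
- Some heroin users would be caught by the fentanyl test, if they have a history that triggers it.
- Criterion 3 has a reading under which the urine result is not always required.
- The TLFB still records heroin use, and opioid-use frequency is generated from it. The plan describes no separate urine model and no rule for correcting the TLFB from urine, so a fuller panel would not by itself correct under-reporting.
- Mass-spectrometry confirmation could be ordered when a reported heroin day meets a negative screen. The text permits that only arguably, since it ties confirmation to the listed substances. It would not help where heroin use is neither reported nor screened for.

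These points limit the strength of the claim. They do not remove the mismatch between the listed assays and the uses the plan makes of urine results.

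**Conclusion.** The concern holds in a limited form. The protocol names no opiate-class assay. If the list is followed as written and the named assays do not cross-react, heroin, morphine and codeine use would go unconfirmed, and the urine measure in the opiate-use domain would miss it. If the missed share is similar in the two arms, the urine comparison is biased towards no difference. The size is not derivable from the documents.

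The entry consequence applies only on the first reading of criterion 3, and only to entrants not on buprenorphine and without fentanyl exposure. The TLFB measure and the primary PTSD aim are unaffected. This should be fixed, but it does not threaten the main question of the trial.

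**What to change.** 1. In the paragraph on confirming self-reported drug use, add an opiate-class (morphine) immunoassay to the panel run on every urine already collected, including screening, at both sites. If the VA panel already runs one, name it so that both sites order the same test.
2. Define opioid-positive for the urine outcome as positive on any listed assay for a non-prescribed opioid, not counting prescribed buprenorphine.
3. Reconcile the urine wording of criterion 3 with the panel and with the admission of people already taking buprenorphine, and make its and/or structure explicit.

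The cost is one further immunoassay per urine, some additional confirmatory tests and a wording amendment. No visit, sample or staff time for collection is added.

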Despite this growing literature, there is a gap in the published research regarding opioid use disorder and comorbid PTSD.[28] There is some evidence that treatment with buprenorphine among those with PTSD leads to an overall improvement in treatment outcomes[28] and an observational study suggests buprenorphine treatment is associated with improvement in PTSD symptoms compared to a control group prescribed high dose opioid therapy.[66] Despite these advances, there are no studies evaluating the combination of opioid substitution therapy with a PTSD evidence-based treatment. This has been identified as an important area of study[28] that the proposed research is intended to address.

Studying an evidence based psychotherapy for co-occurring PTSD among those with comorbid OUD has substantial significance and great clinical relevance. To apply an intervention to a new vulnerable clinical population has a potential to change clinical practice. Most importantly, this study has the potential to fill knowledge gaps and challenge the VA to improve healthcare delivery based on scientific evidence.

We would like to underscore that while we hypothesize that CPT will be safe and effective for Veterans with PTSD and OUD, we believe that we cannot assume this to be true. There is a body of literature that suggests that treatments developed for a single condition, such as PTSD, are not equally effective when used in individuals with comorbidity. For example, medications to treat PTSD including the FDA-approved antidepressant, sertraline and the alpha adrenergic medication prazosin [which are recommended by the VA/DoD practice guidelines [67] for sleep disturbances associated with PTSD] are *not equally effective* when used among individuals with comorbid alcohol use disorders.[68-71] Without well-designed clinical trials conducted in comorbid groups, assumptions about efficacy would have been mistaken. *Particularly with behavioral therapies*, there is controversy regarding the use of evidence-based psychotherapy in individuals with comorbid substance use disorders for fear of precipitating relapse.[62] Studies among those with opioid use disorders maintained on buprenorphine are therefore important. *Clinical trials are needed to show efficacy and safety.*

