Cognitive Processing Therapy (CPT): CPT is a manualized, 12-session 1:1 cognitive therapy that has been designed for patients with PTSD [76]. In this study the sessions will be conducted weekly. The stated goal of CPT is "to assist the client in refraining from assimilating (distorting the event to fit prior beliefs) and in accommodating schemas to the new information without over-accommodating".[77] CPT uses Socratic questioning targeting distorted cognitions such as self-blame, hindsight bias, and other guilt cognitions. CPT is focused on the cognitive components of the therapy without exposure. Therapy will be provided by psychologists who either have been or will be trained in conventional CPT through the VA rollout initiative. [[name] will be responsible for coordinating therapy and therapists will have weekly case consultation/supervision from a qualified CPT consultant ([name], who is a national CPT trainer and supervisor).]

Individual Drug Counseling (IDC): IDC will serve as the control group. The current standard of treatment for individuals entering buprenorphine maintenance is to do drug counseling. In most VA settings, including VA Connecticut Healthcare System, psychiatric symptoms (such as PTSD) are evaluated but psychiatric treatment is often deferred until the individual demonstrates a commitment to treatment and demonstrates abstinence. Standard counseling is the primary means to achieve these goals. IDC uses a semi-structured, time-limited addictions-counseling model in a 1:1 setting. The main focus is on helping individuals achieve and maintain abstinence by encouraging behavioral changes, such as avoiding triggers, structuring one's life, and engaging in healthy behaviors (e.g., exercise). The IDC manual provides an organized, concise version of what is currently practiced by most addiction counselors. In operationalizing this approach, the developers drew from their own clinical experience and that of expert drug counselors in the field. The approach is consistent with the 12-step approach that regards recovery as a gradual process, and participation in self-help groups such as Alcoholics Anonymous or Narcotics Anonymous is strongly encouraged. IDC will be conducted by study personnel and supervised by [name] on a weekly basis.[78]

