Subject Payment. All participants will be compensated for their participation. Participants will be paid \$30 for the initial screening/baseline assessment. They will be compensated \$30 for each medication visit (x7), and \$45 for follow up visits. There will be no payment for therapy sessions. Individuals can receive up to a total of \$330 if attending all scheduled treatment and visits. Payment will be made through electronic funds transfer (EFT). Participants will need to provide us with your banking information by completing a special payment form. Alternatively, if participants do not have a bank account, a check will be mailed to them instead. This check(s) will be mailed to the address they provide us with. Patients may choose to receive gift certificates issued to them for use at the VCS canteen (retail store) or VCS cafeteria here at the VACHS in lieu of EFT/check payment. If a patient chooses to receive payment by gift certificate they will be paid for the telemedicine/telehealth visits they participated in at their next in-person visit (e.g. if they complete weeks 2 and 3 by telephone they will receive gift certificates for weeks 2, 3, and 4 at the week 4 visit). Study payments are subject to withholding for outstanding federal debts (i.e., defaulted student loans, interstate child support, back taxes etc) without notification.

Power analysis: The sample size calculation for our primary hypothesis (change in PTSD symptoms) was based on findings from one of the largest and most comprehensive meta-analysis reports on PTSD treatment to date.[36] The report evaluated N=112 studies and reported on 137 comparisons, using validated PTSD symptom measures. The meta-analysis reported that the *effect sizes* for psychotherapy when contrasted with a control group were consistently large and averaged $g=1.14$. Three studies administered CPT specifically and the overall effect size for those was large and averaged $g=1.69$. For this study we conservatively are basing our calculations on a moderate effect size by Cohen's definition.[95] For the First and Second Primary aim we estimate that with 60 subjects randomized to each group we have 80% power to detect a medium effect size ($f=0.25$) at two-sided alpha level of 0.05, and assuming 25% dropout we will recruit a total of N=160.]

Data Analysis:

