Study data will be collected and managed using REDCap electronic data capture tools hosted at VA CT Healthcare System. REDCap (Research Electronic Data Capture) is a secure, web-based application designed to support data capture for research studies, providing 1) an intuitive interface for validated data entry; 2) audit trails for tracking data manipulation and export procedures; 3) automated export procedures for seamless data downloads to common statistical packages; and 4) procedures for importing data from external sources.

Descriptive statistics and graphs will be used to summarize the data on all randomized subjects. All continuous variables will be examined for adherence to the normal distribution using normal probability plots and Shapiro-Wilk tests. Transformations will be applied if needed. If normality is not satisfied and transformations do not help with achieving normality alternative analytic strategies will be considered such as generalized estimating equations (GEE) or nonparametric methods for repeated measures analysis. Baseline demographic and clinical characteristics for the two randomized groups (e.g., age, gender, severity of PTSD, and opiate use) will be compared using chi-square tests for categorical variables and t-tests or nonparametric tests for continuous variables. If there are baseline differences between study treatment groups, these variables will be used as covariates in the mixed-effects models analyses described below. Drop outs and completers will also be compared on baseline characteristics using the same approach. Between group differences in treatment retention, medication compliance and frequency of the occurrence of side effect symptoms across the treatment period will also be assessed. Residual plots and other diagnostics will be used to assess model assumptions.

The primary analyses will be intent-to-treat but sensitivity analyses on completers and non-completers will also be performed. All statistical testing will be at a two-tailed alpha level of 0.05. *Adjustments for multiple comparisons will be conducted among measures in specific domains. In the case of PTSD symptoms (use of 2 measures, PCL-5 and CAPS-5) and opiate use (use of TLFB and urine toxicology) the level of significance will be adjusted to 0.025.*

Primary and Secondary Hypotheses:

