For the primary and secondary hypotheses, we will use mixed effects models to assess changes in PTSD symptoms and opiate use over time. Treatments will be used as between-subject factors and time (in weeks) will be used as a within-subject factor. The primary outcome variables will be PTSD symptoms as measured by generated from the PCL-5 and CAPS scales. The secondary outcome variables will be frequency of opiate use generated from the TLFB and confirmed with urine toxicology results each medication visit (weeks 1-4, 6, 8, 12) and follow-up. The use of the mixed-effects models approach for the analysis of our longitudinal data has several specific advantages. Unlike traditional repeated measures analyses, mixed effects models allow for different numbers of observations per subject, use all available data on each subject and are unaffected by randomly missing data. They also provide flexibility in modeling the correlation structure of the data.[96]

Primary Aim 1. We hypothesize that CPT will significantly reduce PTSD symptoms compared to IDC in Veterans and civilians with PTSD and comorbid OUD maintained on buprenorphine.

This hypothesis will be tested by the interaction of treatment (CPT vs. IDC), and time in the mixed model specified above. Significantly greater decrease in PTSD symptoms in the CPT group will be considered supportive of the hypothesis.

Secondary Aim 1. We hypothesize that CPT will significantly reduce opioid use compared to IDC in Veterans and civilians with PTSD and comorbid OUD maintained on buprenorphine.

This hypothesis will be tested by the same approach as described in primary aim 1 but with frequency of opioid use as the dependent measure.

Exploratory Hypothesis:

We hypothesize that CPT will significantly improve retention (days in treatment) compared to IDC in Veterans and civilians with PTSD and comorbid OUD maintained on buprenorphine.

This hypothesis will be tested using ANOVA or nonparametric equivalent comparing the two treatment groups (CPT vs. IDC).

We hypothesize that CPT will significantly improve psychosocial functioning (measured by the VR-12 survey) compared to standard counseling in Veterans and civilians with PTSD and comorbid OUD maintained on buprenorphine.

This hypothesis will be tested by the interaction of treatment (CPT vs. IDC) and time.

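### The 80% power claimed for the opioid-use aim has no opioid-specific basis and is stated at alpha 0.05; at the planned 0.025 per measure it is about 68% with 60 per arm

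*Combined protocol and SAP*

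**What the plan says.** All places are in the combined protocol and SAP.

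- **Section 6, Power analysis.** The calculation is introduced as serving the primary hypothesis on PTSD symptoms. Its source is a meta-analysis that "reported on 137 comparisons, using validated PTSD symptom measures", with mean effects of g=1.14 for psychotherapy against control and g=1.69 for three CPT studies. The plan then adopts a moderate effect by Cohen's convention, calls this conservative, and concludes: "For the First and Second Primary aim we estimate that with 60 subjects randomized to each group we have 80% power". The effect assumed is f=0.25, and alpha is 0.05, two-sided. With 25% dropout this gives N=160.
- **Section 3, Specific Aims, and section 6, Primary and Secondary Hypotheses.** There is one primary aim (PTSD symptoms). Opioid use is Secondary Aim 1, framed as superiority: "We hypothesize that CPT will significantly reduce opioid use compared to IDC". It is tested by the treatment-by-time interaction in a mixed model.
- **Section 6, Data Analysis.** For PTSD symptoms (PCL-5, CAPS-5) and for opioid use (TLFB, urine toxicology), "the level of significance will be adjusted to 0.025".
- **Section 6, Experimental Treatments.** IDC is described as the current standard for people entering buprenorphine maintenance. "The main focus is on helping individuals achieve and maintain abstinence by encouraging behavioral changes".

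**The concern.** Three things in the power statement do not fit the rest of the plan.

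1. It covers a second primary aim that no longer exists. Reading this as the opioid-use aim is an inference, but no other candidate is apparent.
2. The argument that d=0.5 is conservative concerns a different outcome and a different kind of comparator. On PTSD symptoms IDC is close to a true control, since the risk section says it leaves those symptoms unaddressed. On opioid use it is the standard active treatment, and both arms also receive buprenorphine and Medical Management. Nothing in the plan indicates how large a CPT-IDC difference in opioid use to expect.
3. Power is computed at twice the significance level at which each measure will be tested.

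A reader would therefore credit the opioid-use aim with more power than the plan supports. This affects how a non-significant result is read. The Significance section reports controversy over using "evidence-based psychotherapy in individuals with comorbid substance use disorders for fear of precipitating relapse". If a non-significant result is thought to come from a test with 80% power, it may be taken as reassurance on that point.

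**Working it through.** **Inputs.** From the Power analysis: 60 per arm, f=0.25, two-sided alpha 0.05, 80% power, 25% dropout, N=160. From Data Analysis: 0.025 per measure. For two equal groups d = 2f = 0.5. Effects are in SD units because the plan gives no SD for opioid use.

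**Step 1: the plan's own figures.**
- Recruitment: 120/(1−0.25) = 160, which reproduces exactly.
- Power, normal approximation: Φ(d·√(n/2) − z). With d·√(n/2) = 0.5×√30 = 2.739 and z = 1.960, this is Φ(0.779) = 78.2%.
- The two-sample t-test (noncentral t, 118 df) gives 77.5%.

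The stated 80% is thus slightly generous even at 0.05. The t-test needs 64 per arm for 80%.

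**Step 2: the level actually planned.** At two-sided 0.025, z = 2.241. The normal approximation gives Φ(2.739 − 2.241) = Φ(0.497) = 69.0%, and the t-test gives 68.0%. The PTSD aim is affected equally, because its two measures carry the same adjustment.

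**Step 3: difference detectable with 80% power, 60 per arm.** The formula is (z + 0.842)·√(2/60), with √(2/60) = 0.1826.
- Alpha 0.05: (1.960 + 0.842)×0.1826 = 0.511 SD (t-test 0.516).
- Alpha 0.025: (2.241 + 0.842)×0.1826 = 0.563 SD (t-test 0.569).

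**Step 4: power if the true effect is smaller (t-test, 60 per arm).** Values of d below 0.5 are assumptions that show a range.

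| d | alpha 0.05 | alpha 0.025 |
|---|---|---|
| 0.5 | 77.5% | 68.0% |
| 0.4 | 58.4% | 47.1% |
| 0.3 | 37.1% | 26.9% |
| 0.2 | 19.2% | 12.4% |

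**Step 5: what a null result leaves open.** The half-width of the 97.5% interval is 2.241×0.1826 = 0.409 SD (0.41 with the t quantile as well). An estimate of exactly zero would still be compatible with opioid use worse under CPT by about 0.4 SD.

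**Step 6: sensitivity to n (d=0.5, alpha 0.025, t-test).** The design overview gives 30% dropout instead of 25%. Then 160×0.70 = 112, or 56 per arm, and power is 64.6%. If all 80 randomized per arm contributed in full, it would be 81.5%.

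**Step 7: sensitivity to the repeated-measures model.** As an illustration, take a change-score comparison with baseline-outcome correlation ρ. It replaces d by d/√(2(1−ρ)). At alpha 0.025 and 60 per arm (normal approximation), power is 53%, 69% and 90% for ρ = 0.3, 0.5 and 0.7. The plan gives no ρ, so the direction of the departure from Step 2 is unknown.

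**The case against.** **The 80% is a conditional statement.** It is computed from Cohen's f=0.25, not from g=1.14 or g=1.69, and power to detect 0.5 SD does not depend on the outcome or the comparator. This stands. The meta-analysis supports only the word conservative, and that support does not extend to opioid use. The objection does not rescue the alpha.

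**The mixed model uses partial data.** Dropouts contribute, so the effective size lies somewhere between 60 and 80 per arm, and correlations may help. This is fair, but the plan states its power at 60 per arm and gives no correlation.

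**The plan does give a reason to expect an opioid benefit.** The Significance section links PTSD improvement to better substance-use outcomes and cites the group's own pilot data in OUD. The background also says CPT has room to address thoughts about drug use. These statements are there, but the OUD data shown are three-month retention in a retrospective chart review (10/10 against 11/36, by referral status) and PCL scores in five patients. Neither is a measure of opioid use.

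**Stronger readings a reader might infer.** One is that the opioid comparison will probably end null. The documents do not support this: a null is more likely than not only if the true effect is below about 0.36 SD (alpha 0.05) or 0.41 SD (alpha 0.025), and the plan neither states nor excludes that. Another is that the trial cannot say whether CPT costs opioid control. That is too strong: testing is two-sided, so a harm of 0.5 SD would be detected with about 68% probability at 0.025, and an interval bounds the loss. A third is that a non-inferiority margin is required. For a secondary aim this is a design preference.

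**Conclusion.** The point holds as a correction to the power statement and to how the opioid-use result is read. The statement covers a primary aim that the plan no longer has, and no opioid-use effect, SD or rate supports it. Its alpha of 0.05 contradicts the 0.025 planned for each measure. At the plan's own d=0.5 and 60 per arm, power is about 68% instead of 80%, and the detectable difference is about 0.57 SD. This rests on three assumptions: the second primary aim means opioid use, 60 per arm is the effective number, and a two-group comparison at one time point is a fair stand-in for the mixed-model interaction. The last could move the figure either way. The mismatch in alpha does not depend on any of the three.

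**What to change.** **Power analysis.**
- Remove the reference to a second primary aim.
- For opioid use, state power or detectable difference at 0.025 (about 68% at d=0.5, or about 0.57 SD at 80% power, with 60 per arm). Say that d=0.5 is a convention without opioid-specific support, and that IDC is an active comparator for this outcome.
- Restate the PTSD figure at 0.025 too.
- If the repeated-measures model is expected to recover power, give the assumed correlation and the resulting figure.

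**Primary and Secondary Hypotheses, Secondary Aim 1.**
- Report the CPT-IDC difference for each opioid measure with a 97.5% confidence interval, matching the planned level.
- Add a sentence that a non-significant superiority test is not evidence that opioid control is preserved.

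A prespecified non-inferiority margin is optional and not part of this correction.

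**Cost.** Wording only, with no extra patients, visits or data. The drawback is a less favourable stated power for both aims.
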